Figure 2. Room air filters and airborne Mus m 1 concentrations. 65 homes were randomized to receive bedroom air HEPA filters or no intervention. Airborne Mus m 1 was quantified at baseline and 6 months. Mus m 1 concentrations are depicted on the y-axis and expressed in ng/m³. Intervention (solid line, hollow diamonds), n=34; Control (dashed line, solid squares), n=31; p = 0.26.

that the IPM arm will also have a marked reduction in mouse allergen levels in their homes. Indeed, a pilot study using a similar IPM protocol observed a 75% reduction in home mouse allergen levels by five months post intervention. Several other trials with a focus on cockroach allergen, including one in Baltimore, have also demonstrated substantial reductions in cockroach allergen with an IPM intervention. These studies provide strong preliminary data to support the efficacy of IPM interventions in reducing home pest allergen levels.

(2) **Airborne Allergen Reduction with Air Purifiers:** Furry animal allergens are readily detected in air samples because they are found on small particles, typically those ≤10microns. Air filtration is effective not only in reducing indoor PM, but also furry animal allergens, so will be included as a component of our ECS intervention. For example, a

Baltimore-based environmental intervention study indicates that room air purifiers reduce airborne mouse allergen levels. In this study, 65 asthmatic children were randomized to receive either a bedroom filter or no intervention. At six months, airborne mouse allergen levels had decreased by 68% in the intervention group, but had increased in the control group. This marked degree of reduction was achieved even though there was no IPM intervention targeting

mouse infestation in this study. (Figure 2) Other studies have also demonstrated reductions in other airborne animal allergens, including cat and dog.^(17, 18)

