Swabs for microbial assessment: The nares, oropharynx, and skin will be sampled using Copan E-swabs™ (Copan Diagnostics, Murrieta, CA) for staphylococcal culture and Catch-All™ sample collection swabs (Epicentre Biotechnologies, Madison, WI) for bacterial community analysis at CV1,2,3,and 4. The child may self-swab with the help of a parent/guardian.

At HVs: Home Assessment Visits (HV) will occur at baseline, 3 and 6 months. Home inspection, settled dust collection, PM₁₀, PM_{2.5}, airborne allergen measurements, and microbial air sampling may occur at all HVs. The air sampling of microbes and their products will be compared to dust samples collected. PM_{2.5-10} will be calculated, as done in previous studies, by subtracting the PM_{2.5} concentration from the PM₁₀ concentration that is measured adjacent to, and simultaneously with, the PM_{2.5} measurement. A passive filter for air nicotine monitoring will be placed in the home at baseline and 6 months.

Home inspection: A trained technician will conduct a home inspection to collect data regarding the home environment, including condition of dwelling, evidence of tobacco smoking, evidence of pets and pests.

Dust sample collection: Dust will be collected from the bed and bedroom floor using a standard procedure. The dust samples will be analyzed for the major relevant indoor allergens: Mus m 1, Der f 1, Fel d 1, Can f 1, and Bla g 1. A portion of the bedroom dust sample will be saved for future studies. A separate dust sample will be analyzed for bacterial communities and *S. aureus*, including staphylococcal enterotoxin proteins that may be secreted by the bacterium. Additional dust will be collected from standardized home surface sites using sterilized electrostatic cloths (autoclaved Swiffer™, Proctor & Gamble, Cincinnati, OH) for bacterial culture. Temperature and humidity data may also be collected.

If a participant moves between home visits, and the participant is randomized to receive intervention, an attempt will be made to collect another dust sample prior to the intervention visit.

URI Assessment: A respiratory illness questionnaire will be completed at the 3 month (HV2) home visit.

Socioeconomic Questionnaire: A questionnaire about specific socioeconomic factors will be administered at the first home visit.

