Bacterial Questionnaires: At the home visit we may collect data on established risk factors for acquisition of *S. aureus* and other bacteria, such as daycare, gym use, and antibiotic use, and household location (which will be collected on a separate form, then geocoded into X, Y coordinates from address data before linkage with health or demographic data).

Pet Questionnaire: We may collect data on participant contact with and characteristics of pet animals in the home. These data will include notations from visual inspection of the pets and areas of the house related to pets (e.g. pet crates).

Sampling of pets and pests: Under an approved ACUC protocol ([name], SP14H352, 9/18/2014-9/18/2017), Copan Eswabs™ (Copan Diagnostics, Murrieta, CA) for bacterial culture and Catch-All™ sample collection swabs (Epicentre Biotechnologies, Madison, WI) for bacterial community analysis may be collected from all pet animals at multiple anatomical sites and from freshly trapped rodents and other trapped pests. The informed consent process for these pet swabs will be conducted under the approved ACUC protocol and conducted by the [name] group. Study participants randomized to pest control will be given a magnet with a number to call to schedule optional pick-up of freshly trapped rodents and other pests from the home to transport to the laboratory for bacterial sampling.

Particulate Matter and Airborne Animal Allergens: Particulate matter monitoring will be conducted in the child's bedroom using integrated sampling direct-reading methods for an approximate 5 day period. Air samples for PM_{2.5} and PM₁₀ will be collected using methods developed during previous childhood asthma studies.⁽³⁴⁾ After gravimetric analysis, the PM₁₀ filters will be assayed for allergen content in the [name] laboratory. PM₁₀ samples will be analyzed because previous research indicates that the bulk of airborne animal allergens is contained on particles less than 10µm in aerodynamic diameter.^(35, 36) Microbial air sample measurements may be obtained.

Inspirotec air monitors will be deployed in a subset of homes to establish correlation between our PM10 measurements of airborne biomass and Inspirotec spectroscopic measurements of biomass. We will also compare the limits of detection of the two methods and validate the utility of the Inspirotec sampler as easily deployable in home environments.

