The primary outcome will be the treatment step that is assigned at the final clinic visit at six months. The six month time point has been chosen because successful ECS trials have observed an effect by six months, but an effect may not be observed before this time because it takes several months for indoor allergen levels to fall after implementing an environmental intervention. The secondary outcome will be total daily ICS dose assigned at this same visit, expressed in milligrams. The primary analysis dataset will be an intent-to-treat (ITT) dataset and will include participants with six month outcome data collected, regardless of whether they completed all of the ECS activities. A per-protocol analysis will also be performed and will be performed on the dataset of participants with six month

outcome data who completed at least one intervention visit (one IPM visit or for the Medication Group, receipt of ECS educational materials). Exploratory data analysis for both Aims 1 and 2 will include compilation of descriptive statistics to detect any outliers or discrepancies in data and to compare baseline characteristics and demographics between ECS+Medication and Medication Groups. Continuous variables will be summarized using means, medians, standard deviations, ranges, and interquartile ranges. Continuous variables will be analyzed using non-parametric approaches or will be transformed to meet assumptions of normality required for parametric statistics. Categorical variables will be tabulated. The percent of participants who complete the study, losses to follow-up, missed visits, and reasons for discontinuation will be presented.

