Potential confounders will be explored by examining any differences between the intervention and control groups and also assessing the association between the potential confounders at baseline and at the final study visit. In addition, potential confounders will be included in the models to determine the impact the variables have on the relationship between group assignment and the outcome. Some specific confounders that will be carefully examined include baseline allergen and pollutant levels, treatment step at baseline, and season. Potential effect modifiers, such as baseline pollutant and allergen levels, baseline asthma severity, baseline asthma control, baseline lung function, and number of positive skin tests, will also be examined by stratifying analyses and creating an interaction term to include in the final models. Analyses will be stratified by these potential response predictors and interaction terms will be included in models to determine if any of these factors predict responsiveness to the intervention.

To measure the change in home airborne particulate matter (PM_{2.5} and PM_{2.5-10}) and indoor allergen concentrations (cat, dog, mouse, cockroach, and dust mite) among study participants. Distributional properties of baseline levels of pollutants (PM_{2.5} and PM_{2.5-10}) and allergens will be assessed using histograms and boxplots and any necessary transformations to these variables will be conducted to obtain approximately Normal distributions. We will subtract baseline levels of these exposures from levels recorded 6 months post-randomization to assess the within-person change in exposure over time. Differences over time in the intervention group will be compared to those in the control group via standard *t*-tests using a significance cutoff of 0.05. Assessment of significance adjusting for multiple comparisons will be done using the method of Benjamini and Hochberg.

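### Aim 2a fixes a t-test on transformed allergen change but has no rule for values below the assay limit; if non-detects are common, the usual substitutions understate the reduction and cost power

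*Combined protocol and SAP*

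**What the plan says.** Section 6.c, Analysis Plan, treats particulate matter and the five indoor allergens alike. Baseline distributions are inspected and "any necessary transformations to these variables will be conducted to obtain approximately Normal distributions". The outcome is change: "We will subtract baseline levels of these exposures from levels recorded 6 months post-randomization to assess the within-person change in exposure over time". Arms are compared "via standard *t*-tests using a significance cutoff of 0.05", with a Benjamini-Hochberg adjustment. A general sentence earlier in the same section allows an alternative: "Continuous variables will be analyzed using non-parametric approaches or will be transformed to meet assumptions of normality required for parametric statistics".

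On the assays, the Dust sample collection paragraph says "The dust samples will be analyzed for the major relevant indoor allergens" and lists Mus m 1, Der f 1, Fel d 1, Can f 1 and Bla g 1. Airborne allergen is measured on the PM10 filters. Detection limits are mentioned once, in the paragraph on particulate matter and airborne allergens: "We will also compare the limits of detection of the two methods". That sentence is about comparing two air samplers in a subset of homes. It gives no rule for analysing allergen results.

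The documents give no detection limit, expected share of non-detects, allergen standard deviation or power figure for Aim 2a.

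**The concern.** An assay with a lower limit returns a block of tied values when levels are low. A monotone transformation moves that block but cannot spread it out. A home at the floor at both visits shows zero change whatever happened, and a home pushed below the floor shows only part of its fall. The transformation is also chosen on baseline data, so non-detects that the intervention creates by month 6 would not inform the choice.

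Non-detects are plausible here. Entry needs sensitisation to any one of several allergens. The rodent and cockroach modules (Table 5) also require evidence or a report of infestation, and pets are sampled only where present. The plan therefore expects homes without a given source, yet compares all five allergens. The Background also expects success against mice: in one study "airborne mouse allergen levels had decreased by 68% in the intervention group", a pilot saw a 75% fall in home mouse allergen, and more than 60% of pest-management homes in the ongoing mouse trial had complete eradication. If the intervention works, its arm gathers more non-detects than the control arm.

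The size of each exposure reduction is the result of Aim 2a, and exposure reduction is also the intermediate variable in Aim 2b.

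**Working it through.** **The plan's own figure.** None exists for Aim 2a. The only power figures are those in Table 6, for treatment step. For 1 step, SD 2.0 and 100 per arm, SE = 2√(2/100) = 0.283 and power = Φ(1/0.283 − 1.96) = 0.94, as stated. At n = 175 the calculation gives 0.91 against the stated 0.90. The point here does not touch those figures.

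**Inputs.**
- From the documents: a 68% reduction (airborne mouse allergen, Background) as an illustrative effect; about 87 per arm (175/2, Table 6); 0.05, taken as two-sided.
- Assumed, because the documents are silent: log-normal levels, log SD s = 2, baseline-to-month-6 correlation 0.6, baseline non-detect share p from 5% to 60%, and non-detects set to limit/√2.

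**Apparent reduction.** Centre the baseline log level at 0.
- True shift: δ = ln(1 − 0.68) = −1.139.
- Limit: L = s·Φ⁻¹(p). Substituted value: c = L − ln√2 = L − 0.347.
- Mean recorded log level when the true mean is μ: m(μ) = μ[1 − Φ(a)] + s·φ(a) + c·Φ(a), with a = (L − μ)/s.
- Randomisation makes the baseline means cancel, so the expected difference in change is D = m(δ) − m(0), and the apparent reduction is 1 − e^D.

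Worked case, p = 40%: L = −0.507, c = −0.853.
- Control: a = −0.253, m(0) = 2(0.386) − 0.853(0.400) = 0.431.
- ECS: a = 0.316, m(δ) = −1.139(0.376) + 2(0.379) − 0.853(0.624) = −0.202.
- D = −0.633, so the apparent reduction is 1 − e^−0.633 = 47%.

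| Baseline non-detects | ECS non-detects at month 6, Φ(a) | D | Apparent reduction (true 68%) |
|---|---|---|---|
| 5% | 14% | −1.069 | 66% |
| 10% | 24% | −1.002 | 63% |
| 20% | 39% | −0.874 | 58% |
| 40% | 62% | −0.633 | 47% |
| 60% | 79% | −0.407 | 33% |

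Simulated trials under the same assumptions agree: about 65%, 59%, 46–48% and 33% at 5%, 20%, 40% and 60%. A true 40% reduction appears as 34%, 27% and 19% at 20%, 40% and 60%.

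**Dependence on the substitution.** Separate simulations used log SD 1.5 and 2.5, correlation 0.5 and 88 per arm. With non-detects set to the limit, limit/√2 or limit/2, a true 75% reduction appears as 70–74%, 59–68%, 44–57% and 28–43% at 5%, 20%, 40% and 60% non-detects. Setting them to limit/10 reverses the error at low shares: a true 50% appears as 52–57% at 5–20% non-detects. Excluding non-detects also understates (a true 50% appears as 29–45%) and costs more power. A left-censored model returned 49–51% for a true 50% and 74–76% for a true 75% throughout.

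**Power, true 68%, log SD 2, limit/√2.** Without censoring, the SD of change is 2√(2 × 0.4) = 1.789, SE = 1.789√(2/87) = 0.271, and power = Φ(1.139/0.271 − 1.96) = 0.99.

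| Analysis | 40% non-detects | 60% non-detects |
|---|---|---|
| Planned t-test on change | 0.87–0.90 | 0.70–0.71 |
| Baseline-adjusted linear model, substituted values | 0.96 | 0.91 |
| Baseline-adjusted censored model | 0.96–0.98 | 0.93–0.95 |

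Baseline adjustment supplies most of the power gain. It does not move the expected size: with balanced baselines the adjusted model still targets D. Only the censoring corrects the size.

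**The case against.** **The effect may be small.** The Background says that the targeted allergens are present at high levels in Baltimore homes, which argues against baseline non-detect shares of 40–60%. At 5% the loss is trivial. With log SD 1.5, power for a 75% reduction stays at 0.95 or more with up to 40% non-detects under the usual substitutions. This stands, and it makes the point conditional. But the statement describes the population, not every allergen in every home, and it does not cover month 6 in the ECS arm.

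**The expected reductions are narrow.** The 68% and 75% figures concern mouse allergen only. The 68% is a within-arm fall, and the figure caption for that study gives p = 0.26. This stands; 68% is used above only as an illustration.

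**The general rule allows non-parametric methods.** It does, but a rank test does not give the size of the reduction. Nor did it restore power: for a true 50% reduction, log SD 1.5 and 40% non-detects, a rank test on change had power 0.58, against 0.85 for the t-test on uncensored data.

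**The censored model can mislead.** Suppose 60% of ECS homes are eradicated and end between limit/4 and the limit (or stay lower), with the rest unchanged. At 40% baseline non-detects the true reduction is about 60%, the t-test gives about 54% and the censored model about 82%. This stands as a reason for sensitivity analyses. It depends on eradicated homes sitting just below the limit: if they fall to between limit/100 and the limit, the censored model gives 82% against a true 83%, and the t-test 54%.

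**Stronger readings.** A reader might infer that the reduction will be understated and power lost. The documents support neither as fact: they give no non-detect share and no substitution rule, and even the direction depends on that rule. A reader might take the detection-limit sentence as acknowledging limits for these allergen assays; it concerns the sampler comparison. A reader might also infer that the ranking of allergens in Aim 2b will be distorted; the plan names principal stratification but does not say how exposure changes enter it or that allergens are ranked.

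**Conclusion.** The concern holds conditionally. The Aim 2a test is fixed and nothing in the plan handles allergen values below the detection limit. If non-detects are frequent and one of the usual substitutions is used, the ECS reduction is understated: under the stated assumptions a true 68% appears as roughly 59%, 47% and 33% at 20%, 40% and 60% baseline non-detects. Power falls with it, from 0.99 without censoring to 0.87–0.90 at 40% and 0.70–0.71 at 60%. With few non-detects the effect is negligible, and with a very small substituted constant the error can go the other way. An unstated coding choice could therefore move the Aim 2a estimate in either direction, which is the main reason to settle it in advance.

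The figures rest on assumed log-normality, log SD, correlation and non-detect share. The point is confined to the allergen results of Aim 2a and the exposure changes carried into Aim 2b.

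**What to change.** For each dust and airborne allergen, replace the unadjusted t-test on change with a regression of month-6 log concentration on arm. Adjust for baseline log concentration and a baseline non-detect indicator, and treat month-6 non-detects as left-censored at the assay limit (for air samples, converted to a concentration using the sampled volume). Report the ratio of geometric means with a 95% CI, the detection limits, and the share of non-detects by arm and visit.

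Because complete eradication could break the assumed log-normal tail, pre-specify three sensitivity analyses: the same baseline-adjusted model with one fixed substitution, a rank-based test, and a comparison of the proportion detectable. Use the same non-detect handling for the exposure changes that enter Aim 2b.

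The cost is SAP wording and a standard model, with no new data. The downside is reliance on log-normality below the limit, where the data cannot confirm it; the sensitivity analyses show how far the conclusion depends on it.

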The power estimate is based on assessment of the primary outcome, treatment step, at 6 months. In the ICAS trial, the ECS resulted in a reduction of 0.8 symptom days/2 weeks within two months of randomization.⁽¹³⁾ The authors of the paper make the point that this effect size is similar to that seen with controller medications. In PREACH, the SHS intervention trial, there was an increase of 1.9 symptom-free days/2 weeks at six months in the group receiving air purifiers compared to the control group. This effect, which was observed with air purifiers alone and no other environmental intervention, is also similar in magnitude to low dose, inhaled corticosteroids, which resulted in an increase of 2 symptom-free days/2 weeks compared to placebo among children with persistent asthma (CAMP).⁽⁹⁾ With a multi-faceted intervention as proposed for this study, we expect a significantly larger effect size than observed with air purifier deployment alone. In terms of treatment step, low dose ICS is one “step-up” from no controller medication, which reflects the difference in controller medication requirement that our proposed study is powered to detect. Further, a 1 step reduction in controller medication requirement would also be the point at which an ECS would likely be cost effective. For example, in the ICAS trial,⁽¹³⁾ the intervention, which was effective for two years, cost approximately \$1500, similar to the cost of a one year supply of low dose ICS. There will be 7 possible treatment steps (Table 6) and, based on the distribution of participants across treatment steps in other studies, we will assume a mean treatment step of 4.0 at baseline among participants in both groups and have estimated the power to detect a difference of 1 treatment step between the two groups, with a standard deviation between 1.5 and 2. With a sample size of 200, and assuming alpha=0.05, we will have a power of 0.94 to detect a difference of this magnitude. With a drop-out rate of ~12%, there will be a power of 0.90. (Table 6)

Treatment step difference	SD	Power for n=200	Power for n=175
0.75	1.5	0.94	0.90
	2.0	0.75	0.69
1.00	2.0	0.94	0.90
	2.5	0.80	0.74

Analysis Plan

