The primary outcome will be the participant's assigned treatment step at the six month clinic visit (as described above). Secondary outcomes include: (1) daily inhaled corticosteroid dose, (2) allergic inflammation markers (allergen-specific IgE, FENO₂), (3) measures of asthma control (days of short-acting beta agonist use, days of slowed activity due to asthma, days of exercise-induced symptoms, days of cough without an upper respiratory infection, nights of waking due to asthma symptoms), and (4) measures of exacerbations (oral corticosteroid bursts, hospitalizations, emergency department visits, and unscheduled physician visits). Other secondary outcomes include FEV₁/FVC, % change in FEV₁ after albuterol, and asthma severity, as measured by the CASI.⁽²⁹⁾ We will subtract baseline levels of the treatment step from the step assigned at the 6 month CV to assess the within-person change in treatment step over time. Differences over time in the intervention group will be compared to those in the control group using a generalized linear modeling approach and a significance cutoff of 0.05. Assessment of significance adjusting for multiple comparisons will be done using the method of Benjamini and Hochberg.⁽³⁷⁾ Regression models will be used to adjust for potential confounders and to test for interactions with potential effect modifiers. A similar analytic approach will be used for other clinical and inflammation outcomes, with appropriate statistical tests and models for the different types of outcome variable data, such a Chi-Square test and logistic regression for dichotomous outcomes.

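### Aim 2a compares arms by a t-test on the 6-month exposure change with no baseline covariate: valid, but in large samples never more precise than adjusting for the baseline level

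*Combined protocol and SAP*

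**What the plan says.** The Aim 2a paragraph of section 6.c (Analysis Plan) transforms exposures where needed towards normality and defines the outcome: "We will subtract baseline levels of these exposures from levels recorded 6 months post-randomization to assess the within-person change in exposure over time". It continues: "Differences over time in the intervention group will be compared to those in the control group via standard" t-tests at a 0.05 cutoff, with Benjamini-Hochberg adjustment. It names no covariate.

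Earlier in section 6.c the plan does provide for adjustment: "Regression models will be used to adjust for potential confounders and to test for interactions with potential effect modifiers". On the covariates it says: "Some specific confounders that will be carefully examined include baseline allergen and pollutant levels, treatment step at baseline, and season". That text follows the treatment-step model and is extended to the other clinical and inflammation outcomes. Baseline exposure enters there as a covariate for asthma outcomes. Nothing ties it to the separate comparison in which exposure is itself the outcome.

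On sampling, Study Procedures section 3.a says: "Home Assessment Visits (HV) will occur at baseline, 3 and 6 months". The visit schedule marks dust and air sampling at HV-1, HV-2 and HV-3, and HV-1 precedes randomization. Section 6.c names no particulate or allergen analysis that uses the 3-month values.

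**The concern.** Aim 2a is the first link in Aim 2: did the intervention lower each exposure? It covers two particulate fractions and five allergens, so at least seven outcomes under a multiplicity adjustment. The documents give no power for any of them.

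A change score does use the baseline, but with a fixed slope of 1. Where the 6-month level tracks the baseline only loosely, subtracting it adds noise. At r = 0.3 with equal variances the change has variance 1.4, against 1.0 for the 6-month level alone. At stake are wider confidence intervals than the collected data allow, and some risk of missing a real reduction in a variable exposure.

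**Working it through.** **Inputs from the documents.** 200 children randomized 1:1. For the sample after drop-out, the power section says "With a drop-out rate of ~12%, there will be a power of 0.90", and its table uses n = 175, or 87.5 per arm. Alpha is 0.05, taken as two-sided.

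**Inputs assumed.** The correlation r between the baseline and 6-month level, and k = 6-month SD / baseline SD. Neither is in the documents.

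**The plan's own figure.** The only stated power is for treatment step. For a difference of 1.00 and SD 2.0, power = Φ(1/(2·√(2/n)) − 1.96) with n per arm:
- n = 100: Φ(3.536 − 1.96) = 0.942 (stated 0.94).
- n = 87.5: Φ(3.307 − 1.96) = 0.911 (stated 0.90; 0.908 with the noncentral t).

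This reproduces. It does not bear on Aim 2a, for which there is no stated figure to check.

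**Why adjustment cannot lose in large samples.** Write s0 and s1 for the baseline and 6-month SDs. Per-child variances:
- change score: s0² + s1² − 2·r·s0·s1
- baseline-adjusted: s1²·(1 − r²)

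The first minus the second is (s0 − r·s1)², which is never negative. It is zero only when the regression slope of the 6-month level on baseline equals 1. Under randomization both methods estimate the same 6-month difference between arms.

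**Equal variances (k = 1).** The variance ratio, adjusted over change score, is (1 − r²)/(2(1 − r)) = (1 + r)/2. The last column is the number of children the change score needs to match adjusted precision at 175, that is 175/ratio.

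| r | change score 2(1−r) | adjusted 1−r² | ratio | SE ratio | n needed |
|---|---|---|---|---|---|
| 0.3 | 1.40 | 0.91 | 0.65 | 0.806 | 269 |
| 0.5 | 1.00 | 0.75 | 0.75 | 0.866 | 233 |
| 0.7 | 0.60 | 0.51 | 0.85 | 0.922 | 206 |
| 0.9 | 0.20 | 0.19 | 0.95 | 0.975 | 184 |

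**Unequal variances.** Ratio = k²(1 − r²)/(1 + k² − 2rk). At r = 0.3, 0.5, 0.7:
- k = 0.8: 0.502, 0.571, 0.628
- k = 1.25: 0.784, 0.893, 0.981

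The extremes give 175/0.502 = 349 and 175/0.981 = 178 children.

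**Validity check.** Simulation with no effect (4,000 trials, 88 per arm, k = 1) gave type I error of 0.045, 0.052 and 0.045 for the change-score t-test at r = 0.3, 0.5, 0.7, with no bias. The simulated variance ratios were 0.652, 0.775 and 0.850, against 0.65, 0.75 and 0.85 in theory.

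**The case against.** The test is valid, the aim is secondary, and the expected effects are large. The Background section cites about a 50% particulate reduction with air purifiers, a 68% fall in airborne mouse allergen and a 75% fall in home mouse allergen, and expects the combined strategy to do better than single interventions. Suppose a 50% reduction is the between-arm difference, so ln 2 = 0.693 on the log scale. With an assumed log-scale SD σ, n = 175 and unadjusted 0.05, power is Φ(0.693/√(V·σ²·2/87.5) − 1.96), where V is 2(1−r) or 1−r²:
- σ = 1.0, r = 0.3: 0.97 for the change score, 0.998 adjusted.
- σ = 1.5, r = 0.3: 0.73 against 0.89.
- σ = 1.5, r = 0.7: 0.98 against 0.99.

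This stands. For effects of that size, power gains matter mainly where exposure is very variable and r is low. Elsewhere the benefit is a narrower interval: 19%, 13%, 8% and 2.5% narrower at r = 0.3, 0.5, 0.7 and 0.9 with equal variances.

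A reader might also infer that the unused 3-month samples are a serious gap. The documents do not support that. The plan justifies month 6 on the ground that "it takes several months for indoor allergen levels to fall after implementing an environmental intervention". HV-2 also comes before Interventions 3 and 4, which bring the second bedding change and the second targeted cleaning. A month-3 value therefore measures a partly delivered intervention.

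**Conclusion.** The point holds as one of efficiency. The planned Aim 2a test is unbiased and keeps its error rate, but it discards precision that the baseline sample already provides. The variance of the 6-month contrast could be cut by 35%, 25%, 15% or 5% at r = 0.3, 0.5, 0.7 or 0.9 with equal variances. Over k = 0.8 to 1.25 and r = 0.3 to 0.7 the cut runs from about 50% down to about 2%. All of these rest on assumed r and k. The equivalent sample of 206 to 269 children needs equal variances and r between 0.3 and 0.7; with the wider range of SDs it is 178 to 349.

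Two stronger readings are not supported:
- A reader might infer that the regression paragraph already covers Aim 2a, or conversely that the t-test is an error. Neither follows: that paragraph concerns clinical and inflammation outcomes, and the t-test is valid.
- A reader might infer mis-timing bias, because HV-3 and CV-4 share the same month-6 window with no required order. The documents give no distribution of visit dates. Order would matter only for the Aim 2b causal analysis, which section 6.c does not describe, so there is no stated analysis to fault or amend.

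No stated figure changes, and the primary outcome is unaffected.

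**What to change.** In the Aim 2a paragraph of section 6.c, replace the t-test on the change by a linear regression (ANCOVA), for each transformed exposure, of the HV-3 level on arm and HV-1 level. Keep the 0.05 cutoff and the Benjamini-Hochberg adjustment. This one covariate delivers all of the gain computed above; a more elaborate repeated-measures model is not needed for it.

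Optionally, report the same baseline-adjusted contrast at HV-2 as supportive only. State with it that allergen may not yet have fallen by month 3 and that Interventions 3 and 4 are still to come.

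The cost is plan wording. Every sample is already scheduled. No child is lost through the covariate, because a child without an HV-1 value has no change score either. The optional month-3 contrast adds secondary tests, and the gain from adjustment may prove small if r is high or follow-up values are more variable than baseline.
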